3. OBJECTIVE

The primary objectives are to compare Collagenase Santyl ointment with Bacitracin ointment in the proportion healed at 3 weeks after initiation of treatment, time to healing (in weeks), and incidence of burn wound infection. The secondary endpoint is scar assessment scores at 90 and 180 days after the initiation of treatment.

Exploratory endpoints are number of burn wounds open compared to number of burn wounds closed and cutometer values at each scar assessment visit.

4. TEST ARTICLES

4.1 IDENTIFICATION

Test Articles:

1) Collagenase Santyl Ointment

A sterile, enzymatic debriding agent which contains 250 collagenase units per gram of white petrolatum, USP.

2) Bacitracin Zinc Ointment

One gram is equal to 500 bacitracin units; one unit of bacitracin is equivalent to 0.026 milligrams.

4.2 USAGE

Santyl and bacitracin will be applied daily to the thickness of a nickel (2 mm) on the burn until the wound heals, with a maximum application period of six weeks.

5. SUBJECTS

5.1 SUBJECT POPULATION

Up to 80 study subjects, aged 2-75 years who meet all study inclusion and exclusion criteria, will be enrolled.

5.2 INCLUSION CRITERIA

Subjects will be considered qualified for enrollment if they meet the following criteria:

- Provide written informed consent, which will consist of reading, signing, and dating
 the informed consent document after the Investigator, sub-Investigator or other
 designated study staff member has explained the study procedures, risks, and contact
 information. For subjects not able to provide informed consent (e.g., minors), a parent
 or legally authorized representative must provide consent. Assent must be provided as
 required by the IRB.
- 2. Age 2 75 yrs, either sex, any race.
- 3. Have one or more acute burns which:
 - are thermal, chemical or electrical in etiology
 - in aggregate cover <10% TBSA
 - are each ≤ 72 hrs old
 - are each no more than deep partial thickness (2nd degree)
 - are not visibly infected
- 4. Able to take in oral fluids.
- 5. Able to comply with the requirement for daily dressing changes, or have a caretaker who is able to comply.
- 6. Willing to make all required study visits.

5.3 EXCLUSION CRITERIA

Any one (1) of the following criteria will disqualify a potential Subject from participation in the study:

- 1. Contraindications or hypersensitivity to the use of the test article or their components (e.g., known hypersensitivity to bacitracin).
- 2. Embedded foreign bodies in the burn wound which cannot be immediately removed.
- 3. The burned tissue includes or is within 1 cm of the eye or genitalia.
- 4. Severe perioral burns.
- 5. Airway involvement or aspiration of hot liquids.

- 6. Suspicion of physical abuse.
- 7. Burn wound requires a skin graft.
- 8. Outpatient management of the burn wound is not appropriate.
- 9. Participation in another investigational clinical study within thirty (30) days of the Screening Visit.
- 10. The Investigator may declare any subject ineligible for a valid medical reason.
 - . Current or recent (< 6 months) history of severe, unstable, or uncontrolled neurological, cardiovascular, gastrointestinal, hematological, hepatic, and/or renal disease or evidence of other diseases based upon a review of medical history that, in the opinion of the Investigator, would preclude safe subject participation in the study.
 - 11. Test articles are cost-prohibitive for subjects

6. STUDY DESIGN

6.1 STUDY DESIGN

This is an active comparator, parallel group study in which subjects with burns meeting the study criteria will be randomly assigned to outpatient treatment with Santyl or bacitracin in a 1:1 ratio. Subjects who appear eligible will be presented with the study, and consent / assent will be obtained prior to any study procedures being conducted. The safety variables include adverse events and, specifically, burn wound infection or allergic contact dermatitis during treatment. Efficacy variables include time to complete healing and scar appearance. Both the Investigators and the subjects will contribute to these evaluations.

Enrolled, randomized subjects will be prescribed with test article (Santyl or bacitracin) and burn wound dressing supplies sufficient to last until burn wound has healed. Scar assessments will occur at 3 months and 6 months post burn healing.

Recruitment bias will exist, as any subject with a known contact dermatitis to bacitracin will be excluded. This will artificially reduce the number of allergic contact rashes in the bacitracin group, but the effect on the primary endpoint is unlikely to be significant. Study Procedure

For a summary of the required procedures by visit, refer to Table 12: Study Plan.

6.2 VISITS AND EXAMINATIONS

6.2.1 Visit 1 – Presentation for Evaluation and Treatment

- 1. Explain the purpose and nature of the study, and have the subject or the subject's legally authorized representative **read**, **sign**, and **date** the IRB-approved informed consent document. In addition, the informed consent document must be signed and dated by the individual who consents the subject. Provide a photocopy of the signed informed consent document to the subject or subject representative, and place the original signed document in the subject's medical record. If the subject is unable to read or sign the informed consent, unable to comprehend the information provided in the consent process, or is younger than the legal age of consent, the parents, legal guardian, decision making proxy or next of kin must provide written consent, and the subject must provide assent as required by the IRB.
- 2. Determine the etiology, extent (TBSA), age (date of burn and number of hours since burn), burn depth, burn wound perfusion measurement with laser Doppler, and location of the burn. Use the provided figure for estimation of TBSA (Appendix 13).
 - If there are multiple burn wounds on a subject, the TBSA for all burn wounds combined must be <10%. Each burn wound must meet study criteria, only the data from the largest burn wound ("target wound") will be recorded in the case report forms and utilized for data analysis. If two or more burn wounds are within 1 cm of each other, the burn wounds can be evaluated as if they were a single burn wound.
- 3. Photograph the burn per standard of care.
- 4. Determine the Fitzpatrick skin type (refer to Section 13).
- 5. Obtain demographic information and medical history, including information on all concomitant medications.
- 6. Perform any required procedures for standard burn care (e.g., debridement, pain relief, tetanus vaccination).

- 7. Obtain baseline measures of the burn wound bed, including the area (in cm²) of the target wound. These measures include exudate type and amount, odor, presence of eschar, presence of epithelial islands, epithelialization of the burn, peri-burn skin characteristics, pain, itching, and state of the burn wound (must be "open"). Refer to Section 13 for details.
- 8. If the subject meets all of the inclusion criteria, the subject should be randomized.
 If the subject does not meet all of the inclusion, the subject will be considered a screen failure.
- 9. Ensure that the subject has enough test article and dressings to last the subject for 10 days. Dispensed supplies may include sterile tongue depressors (for test article application), Xeroform gauze, gauze, paper tape (as needed), and compression bandage/garment.
- 10. A staff member should apply the test article and the dressings to the burn wound while demonstrating to the subject (or caregiver) the proper application of ointment and dressing(s).

Instruct the subject (or caregiver) that:

- a. Only the ointment and dressings prescribed should be applied to the burn wound during the study.
- b. Application of the study ointment and changing the dressings must occur each day.
- c. Test articles are not to be used on any other person or to treat any other wound.
- 11. Instruct subject (or caregiver) to refrain from using excluded medications, to treat as instructed, and to return to the outpatient burn center for Visit 2 in 7 (± 2) days. Make any necessary arrangements for that visit. Remind subject (or caregiver) to bring all study supplies with them to Visit 2.

6.2.2 Visits 2 to 6 [weekly (±2 days) visits after 1st visit]

- 1. Query subject (or caregiver) regarding any changes in general health and the use of concomitant medications.
- 2. If any adverse events are observed or reported, they must be recorded as instructed in Section 9, *Adverse Events*.
- 3. Assess the burn wound. The assessments include exudate type and amount, odor, presence of eschar, presence of epithelial islands, peri-burn skin characteristics & rash, pain, and itching (refer to Section 13).
 - If it is decided that topical antibiotics will be initiated to treat a burn wound infection, the subject must be discontinued from the study. The use of systemic antibiotics does not require subject discontinuation.
- 4. Evaluate re-epithelialization of the burn wound. Complete the visit based on the status of the burn wound as outlined below.

If the burn wound is not completely re-epithelialized ("open"), complete the following steps:

1. A staff member should apply the test article and the dressings to the burn wound while demonstrating to the subject (or caregiver) the proper application of ointment and dressing(s).

Instruct the subject (or caregiver) that:

- a. Only the ointment and dressings prescribed should be applied to the burn wound during the study.
- b. Application of the study ointment and changing the dressings must occur each day.
- c. Test articles are not to be used on any other person or to treat any other burn wound.
- 2. Instruct subject (or caregiver) to refrain from using excluded medications, to treat the burn wound as instructed, and to return to the office for the next sequential visit.

If the burn wound is completely re-epithelialized ("closed"), complete the following steps:

- 1. Photograph the burn wound per standard of care.
- 2. Only moisturizer (Aveeno with Oatmeal) and compression dressing may be used on the scar until the next scheduled study visit. Moisturizer should be used two times per day and as needed. Compression should be used at all times (approximately 23 hours per day).
- 3. Instruct the subject (or caregiver) to continue avoiding any prohibited concomitant medications and to return for the next evaluation at day 90 (±2 weeks). Any scheduled study visits between the current visit and first scar assessment visit not be completed.
- 4. Instruct subject to return to clinic for follow up scar assessment visits 7-8.

6.2.3 Scar Assessment visits 7 to 8 [90 (± 2 weeks), and 180 (±2 weeks), Days After Visit 1]

- Query subject (or caregiver) regarding any changes in general health and the use of concomitant medications.
- 2. If any adverse events are observed or reported, they must be recorded as instructed in Section 9, *Adverse Events*.
- 3. Per SOC photograph the scar at all visits or at any other visit if the subject is discontinuing.
- 4. Provide subject (or caregiver) with the Subject Scar Assessment Scale and ask them to complete an assessment without input from study personnel beyond simple instructions and explanations of terms (refer to Section 13).
- 5. Ask the subject to rate the pain and itch of the scar (refer to Section 13).
- 6. The Investigator or sub-investigator completes the Vancouver Scar Scale (refer to Section 13).

- 7. Once wound healing is confirmed, the subject (or caregiver) will use compression and moisturizer daily 4 weeks post wound healing. Moisturizer should be used two times per day and as needed. Compression should be at all times (approximately 23 hours per day).
 The subject (or caregiver) will use compression and moisturizer for 6 months after wound healing is confirmed only if instructed by the investigator.
- 8. At all visits, remind the subject (or caregiver) to avoid any prohibited concomitant medications and to return for the next evaluation per the protocol visit schedule.

6.2.4 Unscheduled Visits

Unscheduled exams may be conducted at the discretion of the Investigator with all obtained information recorded in the source documents and on the Unscheduled/Interim Visit pages within the CRF.

6.2.5 Concomitant Medications

A concomitant medication is any drug or substance administered from Day 1 of the study through the last study visit. Any product applied topically to the burn wound (except as specified by the protocol) and/or any product intended or claiming to alter the formation or appearance of a scar (e.g., silicone, steroids, Vitamin E, etc) may not be used during the study. The use of concomitant medication must be recorded on the subject's CRF. Adverse events related to administration of these medications must be documented on the appropriate CRF.

6.2.6 Concomitant Therapy

A concomitant therapy is any therapy administered from Day 1 of the study through the last study visit. Any therapy intended or claiming to alter the formation or appearance of a scar (e.g., use of lasers, cryotherapy, radiation, surgical intervention, etc) may not be used during the study.

The use of concomitant therapies must be recorded on the subject's CRF. Adverse events related to administration of these therapies must be documented on the appropriate CRF.

6.3 DISCONTINUED SUBJECTS

6.3.1 Definition and Procedures

Discontinued subjects are those who voluntarily discontinue participation, who are withdrawn for safety reasons, or who have missed 2 or more consecutive study visits or 3 or more consecutive test article doses so as to be ineligible for continued study participation. Subjects who discontinue the study prior to completing all of the regularly scheduled visits should complete the visit procedures for the visit at which the subject is being discontinued. If appropriate, the Investigator should also advise the subject of subsequent therapy and/or procedures necessary for their medical condition.

6.3.2 Delinquent Subjects

In the case of subjects who persistently fail to return for scheduled visits, three attempts must be made to contact the subject (or caregiver) for the purpose of scheduling an Exit Visit. The third attempt should be via registered mail, return receipt requested. If a subject is unable to return to clinic for the 90 or 180 day assessments the Subject Scar Assessment may be collected over the phone.

6.4 SUBJECT PREGNANCY

Women of child-bearing potential are not excluded from the study, nor is birth control required. Both Santyl and bacitracin are FDA approved products and will be used per their respective package inserts; neither product has any pregnancy precautions. If a woman becomes pregnant during the study, she is not automatically discontinued from study participation. She and the investigator will determine if the potential benefits outweigh the potential risks of continued study participation.

6.5 STUDY METHODS AND MEASUREMENTS

Redcap will be used for data collection. The data to be collected, and the methods of collection, are described below. The exact variables to be measured are detailed in the Appendix section.

6.5.1 Burn Wound Bed Appearance and Rash Evaluation

At each weekly visit, the Investigator will note the appearance of the burn wound bed and surrounding tissue. The variables are exudate, odor, presence of eschar, presence of epithelial islands, and peri-burn skin characteristics. If a rash is observed, the rash will be evaluated separately.

6.5.2 Pain and Itching

Pain and itching will each be measured on a scale of 0-10. The subject will be asked to rate pain and itching as a whole number. The anchor points for pain are 0=no pain and 10=worst pain imaginable. The anchor points for itch are 0= no itch and 10= worst itch imaginable.

NOTE: Data from the pain and itch scales will be recorded in the case report forms for subjects who are age 12 and older.

6.5.3 Burn Wound Closure

At each weekly visit, the Investigator will assess epithelialization (as a percentage of the burn wound). When the burn wound is fully re-epithelialized (i.e., 100%), without drainage and without need of a dressing, the burn wound will be considered "closed".

6.5.4 Laser Doppler

A commercially available instrument (PeriScan, Perimed AB) will be used to measure the perfusion of the burn wound. The data will be obtained per the manufacturer's instructions.

6.5.5 Vancouver Scar Scale

Beginning when the burn wound has fully re-epithelialized, the Investigator or sub-Investigator will assess the appearance of the scar using the Vancouver Scar Scale. The scale and descriptions are found in Section 13.

6.5.6 Subject Scar Assessment Scale

Beginning when the burn wound has fully re-epithelialized, the subject (or caregiver) will assess the appearance of the scar using the Subject Scar Assessment Scale. The scale and descriptions are found in Section 13.

NOTE: Data from the subject scar assessment scale will be recorded in the case report forms for subjects who are age 12 and older.

6.6 SUBJECT COMPENSATION

Subjects will be compensated \$25.00 USD for their time at the confirmation of wound healing visit (last weekly visit) and upon completion of Visits 7 to 8.

7. STATISTICAL DESIGN

7.1 EVALUABILITY

All subjects who receive study medication will be evaluable for the safety analysis. All subjects who are randomized to receive study medication will be evaluable for the intent-to-treat analysis.

Unless specified otherwise, SPSS® Version 10.0 or higher will be utilized to perform the statistical analyses of efficacy and safety measures.

Categorical variables will be summarized in general using frequencies and percentages, whereas continuous variables will be summarized in general using descriptive statistics of number of observations (n), mean, standard deviation (SD), minimum (Min), median, and maximum (Max).

Hypothesis testing, unless otherwise indicated, will be performed at the 5% significance level. All P values will be rounded to four decimal places; P values less than 0.0001 will be presented as '<0.0001' in all tables. All group comparisons from analysis of variance (ANOVA) and/or analysis of covariance (ANCOVA) models will be based on Type III sums of squares. All confidence intervals will be two-sided with 95% coverage.

Missing or invalid data of efficacy assessments will be handled by individual scales or subscales on the basis of each individual assessment. Missing data for individual items will be assessed for each assessment of each scale and imputed with the mean score of the corresponding assessment and rounded up to the nearest integer if the number of items with missing data or invalid is less than or equal to 20% of total item number. Otherwise, the assessment score will be set to missing.

Considering that a subject's burn wound may be healed and/or a subject may discontinue from the study prior to the end of the study period, missing values at each weekly visit due to either burn wound healing or early termination or any other reasons will be imputed in this study prior to deriving the efficacy endpoints for evaluation, using the technique of last-observation carried forward (LOCF). By so doing, a burn wound that heals sooner will be given more weight for efficacy.

7.1.1 Primary Efficacy

The primary objectives of the study include the proportion of subjects with the burn wound healed after 3 weeks of treatment, time (in weeks) to healing, and incidence of burn wound infection.,

Both the proportion of subjects with burn wound healed after 3 weeks of treatment and the time to heal between the two treatment groups will be analyzed using ANOVA. Also, the proportion of burn wounds healed at each of the 5 assessments (visit 2,3,4,5, and 6) between the two treatment groups will be analyzed through a mixed-effect ANOVA. The incidence of burn wound infection observed over the study will be compared between the two treatment groups, using a t-test.

The analysis of the primary efficacy evaluations will be performed for the ITT population.

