2.2 RATIONALE

Outpatient management of partial thickness burns normally involves the application of an ointment, which may contain an antibiotic. Concerns about the promotion of antibiotic resistant staphylococci, combined with known risks of allergic hypersensitivity reactions to certain topical antibiotics, support the exploration of alternative treatments. Bacitracin ointment has been compared against white petrolatum in the management of post-procedural wounds among 922 patients with 1249 wounds (17). No significant difference was observed in infection rates (2% in the petrolatum group vs. 0.9% in the bacitracin group) or healing rates. No patients in the white petrolatum group developed allergic contact dermatitis compared with 4 patients (0.9%) in the bacitracin group. In a separate study of 142 patients, 147 Mohs micrographic surgery wounds on the ear were postoperatively treated with either gentamicin ointment or petrolatum. No significant differences were seen between treatments in the incidence of suppurative chondritis infections (4.76% in the gentamicin group; 6.67% in the petrolatum group), whereas there was a higher incidence of inflammatory chondritis in the gentamicin group (11.90% vs. 3.33% for petrolatum) (18). In the 1990s, the North American Contact Dermatitis Group (NACDG) listed bacitracin among the top 10 allergens, based on skin testing. Approximately 9% of bacitracin tests were positive.

. Bacitracin ointment is selected for this study because it is a standard treatment used by the Investigators, and is widely used in burn care. A significant cost difference exists between bacitracin and other ointments, such as Collagenase Santyl. The therapeutic intent for this study is to see if there is a cost reduction benefit as well as reduction in healing time for two standard of care treatment options for partial thickness burn wounds.

This trial does not include a rigorous evaluation of local infection, as quantitative bacteriology from biopsied tissue would be required, nor does it include a rigorous evaluation of hypersensitivity reactions, as de-challenge / re-challenge or measurement of specific humoral and cellular immune responses would be required. Instead, the appearance of the wound bed and periwound tissue will be evaluated, with

particular attention to the description of any rashes. Clinically diagnosed infections may be treated, but use of topical treatment will require that the subject exit the trial.

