7.1.2 Secondary Efficacy

The secondary efficacy endpoint is to evaluate the effect of daily Collagenase Santyl ointment versus daily Bacitracin ointment on scar appearance at 90 days and at 180 days after the initiation of treatment. The secondary efficacy endpoint is defined as the VSS total score obtained at Visit 7 (Day 90) and at Visit 8 (Day 180).

The treatment effect of Collagenase Santyl ointment versus Bacitracin ointment on the VSS total scores will be obtained at each of the two post-healing assessment time points, using analysis of variance (ANOVA) for the ITT population. The mixed-effect model will utilize SPSSPROC MIXED to perform the analysis and define treatment (Santyl vs. Bacitracin) and assessment time point (4 visits: Visits 5, 6, 7 and 8) as well as their interaction as fixed effects, and subject as a random effect. The option of variance components will be used to define the covariance structure of the model.

In addition, a model-based t-test comparisons between Santyl vs. Bacitracin will be performed for each of the 2 assessment time points (or visits).

The null hypothesis states that there are no differences between the two treatments, with the alternative of non-zero differences. The type I error rate for rejecting a null hypothesis will be set at an alpha level of 0.05.

Prior to conducting the analysis, those VSS total scores that are obtained at the early termination visit will be assigned to the next scheduled study visit.

The analyses of the primary efficacy evaluations will also be performed for the PP population.

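### Three primary endpoints are each tested at 5% with no order, alpha split or success rule; if any one significant result counts, the false-positive rate is roughly 7.5–14% under assumed inputs

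*Combined protocol and SAP*

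**What the plan says.** The synopsis, Section 3 and Section 7.1.1 name the same three primary items: share healed at 3 weeks, time to healing, and incidence of burn wound infection. Section 3 begins "The primary objectives are to compare Collagenase Santyl ointment with Bacitracin ointment in the proportion healed at 3 weeks after initiation of treatment" and continues with the other two. Section 7.1.1 opens "The primary objectives of the study include the proportion of subjects with the burn wound healed after 3 weeks of treatment".

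On the significance level, Section 7.1 says: "Hypothesis testing, unless otherwise indicated, will be performed at the 5% significance level". Section 7.1.1 indicates nothing else. It assigns ANOVA to the two healing endpoints and a t-test to infection, and adds a mixed-effect ANOVA of the proportion healed at Visits 2 to 6 without saying how that ranks. Section 8 uses a two-sided 0.05, and 7.1.2 states a non-zero alternative.

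On populations, 7.1.1 assigns the primary analysis to ITT. Section 7.1.2 then says: "The analyses of the primary efficacy evaluations will also be performed for the PP population".

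Section 6.1 describes the variables differently: "The safety variables include adverse events and, specifically, burn wound infection or allergic contact dermatitis during treatment", and then "Efficacy variables include time to complete healing and scar appearance". In discussing recruitment bias it refers to one unnamed endpoint: "but the effect on the primary endpoint is unlikely to be significant".

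**The concern.** With three primary endpoints, a plan has to say what pattern of results counts as success. If one significant result is enough, three tests at 5% give a combined error rate above 5%. If all three are needed, the rate is far below 5%. The plan chooses neither, so the trial's error rate is not defined and the choice could be made after results are seen. The synopsis lists no blinding, which makes it more important to fix the rule early.

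Section 6.1 adds to the uncertainty. Infection is a primary efficacy endpoint in 7.1.1 and a safety variable in 6.1, so it is unclear which kind of claim an infection difference would support. The single primary endpoint mentioned in 6.1 could be any of the three.

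**Working it through.** **Plan's own figure.** The plan gives no overall error rate to reproduce. Its only figure is the 5% level per test.

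**Inputs from the documents.** Three endpoints (7.1.1), 5% per test (7.1), two-sided (Section 8), 40 per group (Section 8). Infection rates of 0.9% and 2% are cited in 2.2, but for post-procedural wounds. Section 9.5 calls burn wound infection frequent without giving a rate.

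**Assumed inputs.** Infection of 5%, 10% and 20%, and the healing distributions. The main ones, as probabilities of healing in weeks 1 to 5 and of remaining unhealed (scored 6), are:
- early (80% healed by week 3): .15/.35/.30/.12/.05/.03
- mid (60%): .10/.22/.28/.20/.12/.08
- late (40%): .04/.12/.24/.25/.20/.15

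Further distributions with 35–95% healed by week 3 were also run, including .30/.40/.20/.06/.02/.02 (90%).

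**Step 1: upper bound.** Three independent 5% tests give 1 − 0.95³ = 14.3%. The two healing endpoints are far from independent, because healing by week 3 is read off the healing time.

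**Step 2: the two healing tests.** With two groups, ANOVA is the two-sided pooled t-test. Simulation under no difference (40 per arm, 60,000–100,000 trials per scenario) gives a correlation of 0.74–0.88 in absolute value between the endpoints. The chance that at least one is significant is 7.4–8.1% with 35–80% healed by week 3, and about 9.0% with 90% healed.

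**Step 3: the infection test.** With 40 per arm:
- 4 versus 0 events: t = 0.10/√[(3.6/78)(2/40)] = 2.08, above the critical 1.99.
- 3 versus 0 events: t = 0.075/√[(2.775/78)(2/40)] = 1.78, not significant.

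At least 4 versus 0 is therefore needed. At 2% infection, P(0 events) = 0.98⁴⁰ = 0.446 and P(≥4) ≈ 0.0082, so the size is about 2 × 0.446 × 0.0082 = 0.7%.

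**Step 4: any of three.** If infection is independent of healing, the rate is 1 − (1 − healing rate)(1 − infection size). Examples:
- healing 7.6%, infection 2%: 1 − 0.924 × 0.993 = 8.2%
- healing 7.6%, infection 10%: 1 − 0.924 × 0.941 = 13.1%
- healing 9.0%, infection 10%: 1 − 0.910 × 0.941 = 14.4%

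Simulated results, with infection independent of healing or correlated with it:

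| Infection rate | Size of infection test | Any of three, 35–80% healed by week 3 | Any of three, 90% healed |
|---|---|---|---|
| 0.9% | 0.06% | 7.5–8.0% | 8.9–9.1% |
| 2% | 0.7% | 8.2–8.6% | 9.6–9.7% |
| 5% | 4.3% | 11.3–12.0% | 12.7–12.9% |
| 10% | 5.9% | 12.8–13.5% | 14.2–14.3% |
| 20% | 5.1% | 12.0–12.7% | 13.3–13.6% |

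Leaving unhealed wounds out of the time analysis adds at most about 0.8 point.

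**Step 5: other rules, early, mid and late distributions.** Requiring all three gives at most 0.4%. Holm on three gives 2.6–4.1% and Holm on the two healing endpoints 3.9–4.2%.

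**Step 6: power.** Early versus mid (80% versus 60% healed by week 3), infection 10% in both arms:
- at least one of three significant: 63.7% unadjusted, 44.0% with Holm on three
- at least one healing result significant: 61.5% unadjusted, 49.8% with Holm on two

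**The case against.** The strongest reply is that the inflation depends on a rule the plan never states. That is correct: a reader might infer that the trial's error rate is 14%, and the documents do not support it. They leave the rule open. The defect is the missing rule, and the figures show what one natural reading of it costs.

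The size also rests on invented inputs, and one protocol rule was left out of the simulation. Section 6.2.2 discontinues a subject whose infection is treated with topical antibiotics, and 7.1 then carries the open status forward. In the extreme case where every infected subject exits unhealed, the any-one rate is 9.9–12.6% at 5–20% infection. This takes the lower end slightly under 11%, but the inflation remains. The decimals should not be relied on.

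Three other inferences go too far:
- *That 6.1 contradicts 7.1.1.* Both lists in 6.1 are worded as non-exhaustive, and an outcome can be a safety variable and a primary objective. The wording adds ambiguity, not contradiction.
- *That the sponsor may pick whichever of ITT and PP succeeds.* Section 7.1.1 names ITT, and 7.1.2 adds PP as a further analysis, so ITT naturally leads. That 7.1 does not define PP is a separate gap.
- *That 2.2 settles the hierarchy.* It says "The therapeutic intent for this study is to see if there is a cost reduction benefit as well as reduction in healing time", but this is rationale covering cost as well, and it ranks no endpoints.

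Taking infection out of the primary family would change an objective stated in three places. That choice belongs to the sponsor.

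**Conclusion.** The concern holds in conditional form. Three primary endpoints share no order, alpha split or success rule, and each is tested at 5%. If any one significant result in either direction counts, the false-positive rate is roughly 7.5–10% at 0.9–2% infection and 11–14% at an assumed 5–20%, or about 10–12.6% in the extreme discontinuation case at those higher rates. The range rests on 40 per arm, assumed healing distributions, and infection rates that are either assumed or borrowed from wounds other than burns. The by-visit mixed-effect ANOVA is not included. Whatever the exact figure, the plan does not define what a positive primary result is. This should be corrected before between-group results are examined.

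**What to change.** Add to 7.1.1, before between-group results are examined:

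> The three primary endpoints (healed at Day 21, time to healing, burn wound infection) are tested in the ITT population with the Holm procedure at an overall two-sided level of 5%. A primary claim is made only for an endpoint that is significant after adjustment. Infection is always reported with its estimate, 95% confidence interval and P value, whatever the healing results. The by-visit mixed-effect ANOVA and the PP analyses are supportive.

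Holm compares the smallest P value with 0.05/3 = 0.0167, the next with 0.025 and the largest with 0.05, stopping at the first that fails.

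If the sponsor decides that infection is a safety outcome, as 6.1 suggests, Holm may instead cover the two healing endpoints only, with the synopsis, Section 3, 6.1 and 7.1.1 reconciled. Infection is still reported in full. In either case, name in 6.1 the endpoint meant by the singular reference.

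**Cost.** A few sentences and matching edits, with no new data or subjects. At the assumed 80% versus 60% healed, the chance of at least one significant primary result falls from about 64% to 44% (Holm on three), or of at least one significant healing result from about 62% to 50% (Holm on two). With Holm on three, detection of an assumed 30% versus 10% infection excess with no healing difference falls from 63% to 44%, which is one reason to report infection unconditionally. With Holm on two, infection keeps its own unadjusted false-positive chance (up to about 6%), and fewer infections alone would no longer be a primary success.
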